 - i. Examples include flavored milks, Capri Sun, Sunny-D, lemonade, Starbucks bottled Frappuccino, bottled yogurt drinks (Danimals, Yakult), fruit punch, Hugs, soda and any other drink with added sugar. Alcoholic beverages are counted as 'other sugary drinks'.
 - ii. If you don't know if a drink contains added sugar, write down the details of the drink from the label in your "notes" section, and look it up on the internet immediately after your observation is complete (so you don't forget). You can start by searching the drink here: https://www.fatsecret.com/. If there is an opaque bottle or a container with an unknown liquid, attempt to ask what's the person is drinking or, if it is too busy to ask, classify these beverages as "unknown"
 - iii. Available type categories are:
 - 1. **Water in Reusable Bottle:** Include all water seen in a reusable bottle. If someone fills a reusable bottle at the fountain, you will tally them here and check the 'R' box.
 - 2. **Bottled Water (Single Use)**: Include all water in a single use receptacle.
 - 3. Milk (plain)
 - 4. Milk (flavored): strawberry, vanilla, chocolate, etc.
 - 5. **Diet Soda/Diet Tea**: count only diet sodas and teas that are artificially sweetened, not sugar sweetened
 - 6. 100% Juice: count only non-carbonated juice that appears to be 100% juice
 - 7. **Soda**: count only sugar-sweetened (not diet/artificially sweetened) sodas. This could include fruit flavored sodas (eg, Crush).
 - 8. **Coffee**: any type of hot or cold coffee beverage
 - 9. **Other Sugary Beverages**: Any other sugary drinks (e.g. lemonade, milkshakes, Sunny-D, Capri-Sun, sweetened teas)
 - 10. Unknown: count coffee mugs or opaque bottles
 - 11. *Note*: We should be able to aggregate these tallies to help us estimate potential trashed saved.
- i. **Notes:** please describe if anything unusual occurs during your shift that might impact water consumption i.e. a parade, a school field day, a birthday party, construction, rain, a holiday, etc. If the fountain is dirty or clogged or broken today, please describe how (e.g., fountain is clogged with sand; trash in the basin). You can use this space to also describe anything else noteworthy (e.g. two small children tried to drink from fountain but couldn't reach; woman washed her hands in fountain; children sat/climbed on fountain)

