Hydrate Philly Research Protocol

Table of Contents

Study Design	
Center Eligibility Criteria	
Center Recruitment:	
Informed Consent:	
Randomization	2
Water Safety Testing	2
Procedures	
Measures	
iviedsures	
References	
List of Appendices	5
A. Water Safety Testing Protocol	6
B. Paper Backup Data Collection Form	
C. Quick Data Collection Guide	11
D. Beverage Intake Questionnaire	
E. Fountain Observation Protocol	13
F. Fountain Observation Form	19
G Fountain Maintenance Survey	20

Study Design

The study is a group randomized trial with n=28 centers. Philadelphia Parks and Recreation (PPR) and Get Healthy Philly (GHP) are partnering to implement the proposed study. All proposed study design and materials have been reviewed and approved by leadership within both organizations and found to comply with other relevant city policies and procedures.

Center Eligibility Criteria

For recreation centers to be eligible to participate in Hydrate Philly they must meet the following criteria:

1. Location in a low-income neighborhood in the City of Philadelphia, defined by ≥20% of the residents in the zip code at or below Federal Poverty Level;

- 2. Site includes both summer and after-school programming
- 3. Willingness to comply with City of Philadelphia Healthy Vending standards and discourage SSB consumption
- 4. Water lines appropriate for installing indoor hydration stations
- 5. Willingness to accept randomization

Center Recruitment:

Project staff will call potentially eligible recreation center leaders and notify them of the opportunity to participate. Project staff will describe the project using an FAQ and sign a Memorandum of Understanding, emphasizing what centers will be requested to do (programming and measures) and what support and resources will be provided to them (equipment, measurement tools).

If more recreation centers are eligible and interested than slots are available, 28 centers will be randomly selected to ensure fairness. A pilot site will be selected by PPR and project staff according to their suitability to start a pilot program in the summer of 2017 to inform the broader program development to be implemented in full in the summer of 2018.

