To minimize staff burden, one staff person per center will be identified to serve as the liaison. City employees are prohibited from accepting gifts, inclusive of incentives for participating in additional work for a research study. The staff liaison will be allowed to decide what center supplies or equipment should be purchased with a \$25 gift card at the end of each measurement period to incentivize the collection of simple measures. This staff person will respond to text-based surveys each weekday with 4 questions (attendance, tally of outside beverages, tally of reusable water bottles, and weight of trash as described above) and fill out a 15-question survey on their own beverage consumption once per measurement period. If the center leader is unable to complete measures by texting or in the case of technical difficulties, paper record backups will be recorded (**Appendix B**). A training on how to complete measures will be performed and a quick reference guide for data collection was developed (**Appendix C**). PPR has used this method of requesting their staff to report on PPR pilot initiatives in the past for program tracking and program evaluation purposes.

Measures

Center water consumption (primary outcome). The primary outcome measure will be each center's total gallons of water taken from hydration stations (or existing water fountains in control centers) as measured by objective water flow meters installed for the study. Water flow meters will be installed before baseline at all sites for all existing operational water fountains, and research staff will record water meter readings at the beginning and end of each 2 weeks measurement period. This estimate will only include water from hydration stations (in intervention sites) or existing water fountains (in control sites) and will not include other non-consumption water use (eg, pools, bathroom sinks, etc). However, some non-consumption water use in water fountains will occur (eg, rinsing cups). In addition, ounces of water per person will be estimated by taking the center level water consumption estimates for 2 weeks and dividing by total attendance.

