Outside beverages during programs (primary outcome). Outside beverages for after-school and summer programs will be measured by the number of youth at the center that bring in an outside SSB or purchase a SSB from the center's vending machine. The center liaison will tally the number of children who bring in beverages each weekday for 2 weeks. Daily tallies will be summed to create one center-level estimate of total outside beverages and will be adjusted for attendance.

Reusable water bottles (secondary outcome/mediator). The center liaison will record the tally of students who brought reusable water bottles to programs following the same approach as outside beverages.

Weight of trash (secondary outcome). Center policies currently require program staff to remove trash daily from after-school and summer program rooms after students leave. Daily program waste will be measured by the center liaison using a portable luggage scale before removing each day for 2 weeks.

Staff SSB consumption (secondary outcome/mediator). At the beginning of each 2-week measurement period and prior to beginning student measures, the staff liaison will complete the Beverage Intake Questionnaire (BEVQ-15; **Appendix D**, (3,4). This questionnaire will be used to estimate staff SSB and water consumption using ounces of water and total energy intake from beverages.

Center attendance (secondary outcome). Attendance will be recorded each weekday by staff for 2 weeks, which is already part of their standard reporting requirements. Any secondary impacts on attendance from the improvement to facilities or change in procedures will be examined. Attendance will also be used as a covariate and as a denominator to estimate water consumption per person.

Fountain Observations. At post, research assistants will conduct observations of the fountain with the flow meter installed (or the new hydration station where the old fountain with a flow meter used to be). **Appendices E & F** describe the protocol in detail and the final observation form.

Maintenance Tracking. Research staff will complete 3-5 calls (lasting approximately 5-10 minutes) during the study period after hydration stations were installed to assess any maintenance

problems (e.g., malfunctioning fountains, vandalism, etc). Surveys will be completed with maintenance staff or site leaders. A survey was developed for the current study (**Appendix G**).

References

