Lead action levels are consistent with the School District of Philadelphia water testing lead action levels and are below the EPA recommended action level of 15ppb for schools and child care facilities designated as a public water system. Notification of elevated levels for other tests will be determined based on EPA criteria for normal ranges that are reported by Penn State Agricultural Analytical Services Lab on each water safety testing report.

If Results are Less than 10 ppb:

10. Inform PPR, PDPH, and recreation site leader of results within 48 hours

[figure not shown]
If Results are 10 ppb or greater:

- 11. Turn off outlet and tag to prevent turning back on
- 12. Notify [name], [name], [name], and [name] of elevated results within 24 hours.
- 13. The city lead program should be notified of elevated lead levels

[figure not shown]
Documentation

- 1. When testing is complete, email notification records should be made to all project staff
 - a. Include:
 - i. Health: [name], [name]
 - ii. PPR: [name], [name], [name], [name], [name],
 - iii. PWD: [name], [name]
 - b. Include PDF of all sites' detailed results and PDFs of all sites' notification letters

Diagram 1

Get Healthy Philly Water Safety Testing Protocol September 2017

elevated lead levels

• HYDRATE PHILLY •

Data Collection Form

Center Name:	

Today's date	1) How many kids attended your program today?	2) How many kids had their REUSABLE water bottles today?	3) How many kids brought in bottled water today, or were given bottled water by staff? Only count DISPOSABLE water bottles here.	4) How many kids brought in SWEET drinks today? (soda, juice, sports drinks, tea, smoothies, etc.)	5) What was the weight of the TRASH for today's summer camp (in pounds)?	6) What was today's reading from your FLOW METER (in gallons)?
EXAMPLE 07/24/2017	28	13	9	14	24.9	871
0172172017						

HYDRATE PHILLY

A Quick Guide to Data Collection

Hydrate Philly will text you for data collection at **3 times** over the next year...

[figure not shown]
Summer 2017: July 24 – August 4

Spring 2018: TBD

Summer 2018: July/August

Every data collection period lasts 10 days. During the period, we'll text you at 3:30 PM every day.

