Here's an example (with made up numbers) of what to expect. **Please respond to our texts using numbers only.** After you respond to the first question, you will receive another text with the second question, and so on until you've answered all 6 questions:

Your responses are NOT monitored as they come in, so if you have questions please contact [name] directly.

Common Questions:

- 1. When do I weigh trash and check the flow meter?
 - Wait until you receive our text at 3:30 PM every day, so you're checking the trash and flow meter at the same time each day. This can be your normal trash take out routine during the data collection period.
- 2. I have more than one trash can. Which trash can do I weigh?
 - Choose the trash can that is most often used for the after school program. The most important thing is to weigh the **same** trash can for the whole data collection period, even if the kids use a different trash can one day.
- 3. What do I do on irregular days, when there are trips or other special events?
 - Keep track of the measures and respond as you normally would. We realize some numbers (for example, weight of trash) may be different than usual on these days.

Instructions: For each beverage below, fill in the bubble for "how often" you drank the beverage IN THE PAST MONTH and "how much" you usually drank.

EXAMPLE: If a person drinks water 5 times per week and drinks about 1 cup each time, they would fill in the bubble for "4-6 times per week" under "how often" and "8 fl oz (1 cup)" under "how much each time."		1. In the past month, how often did you drink the following beverages? (Mark ONE for each beverage)							2. If you drank it, about how much each time? (Mark ONE for each beverage, or skip if you don't drink it)				
		2 times per day	1 time per day	4-6 times per week	1-3 times per week	<1 time per week	Never	6 fl oz (¾ cup or less) Like a small pouch or box	8 fl oz (1 cup)	12 fl oz (1½ cups) Like a typical can	16 fl oz (2 cups)	20 fl oz (2½ cups) Like a vending machine bottle	33.8 fl oz/ 1 liter (4 cups) or more
TYPE OF BEVERAGE												E	
►EXAMPLE: water	0	0	0	•	0	0	0	0	•	0	0	0	0
100% Fruit Juice like orange or apple juice	0	0	0	0	0	0	0	0	0	0	0	0	0
Sweetened fruit drinks like lemonade, punch, Sunny D, Capri-Sun, Tampico (do NOT include 100% juice)	0	0	0	0	0	0	0	0	0	0	0	0	0
Energy drinks like Red Bull or Monster (do NOT include diet)	0	0	0	0	0	0	0	0	0	0	0	0	0

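### The item shown for the SSB primary outcome asks about sweet drinks, names juice, and excludes neither 100% juice nor diet drinks, so it does not match the outcome it feeds

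*Protocol*

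**What the plan says.** The Measures section of the protocol lists outside beverages during programs as a primary outcome. It is measured by "the number of youth at the center that bring in an outside SSB or purchase a SSB from the" center's vending machine. The liaison tallies children each weekday for two weeks. The daily tallies are then summed to one figure per center and adjusted for attendance.

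The collection wording available to the reader is on the Data Collection Form in Appendix B: "4) How many kids brought in SWEET drinks today? (soda, juice, sports drinks, tea, smoothies, etc". This form is the fallback. The Procedures section makes a text survey the main route and says that "paper record backups will be recorded" when texting fails. The example texts in the quick guide (Appendix C) are not reproduced in the copy at hand. The guide says there are six questions, which is also the number of items on the form. The guide's common questions give no rule for classifying drinks. Training is planned, but its content on this point is not described.

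The other two beverage instruments are more specific:

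- Appendix D, the staff questionnaire, has a separate line for 100% fruit juice and tells respondents on the sweetened fruit drink line "do NOT include 100% juice". It also separates diet from regular soda, and unsweetened or diet tea from pre-sweetened tea.
- Appendix E, the observation protocol, has its own 100% juice category ("count only non-carbonated juice that appears to be 100% juice") and its own diet soda and diet tea category. It describes sugary drinks by added sugar.

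**The concern.** The outcome is about SSBs and the item is about sweet drinks. A child with a carton of 100% apple juice is counted, because juice is named and nothing excludes it. A child with a diet soda fits the wording too, since the drink tastes sweet and soda is listed. Tea is listed without a qualifier, which leaves room for doubt. The item also asks only about drinks brought in, so the vending purchases in the outcome definition have no place in it.

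Each day yields one number per center, so juice and diet drinks cannot be removed afterwards. At stake is what a primary result means: a change in this tally is a change in sweet drinks brought in, and reporting it as a change in SSBs goes beyond what was measured. The size of the SSB effect may also be misstated, in a direction that depends on what happens to the other counted drinks.

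**Working it through.** The main finding comes from setting the texts side by side and needs no number:

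| Drink | Outcome (Measures) | Item 4 (Appendix B) | Appendix D | Appendix E |
|---|---|---|---|---|
| 100% juice | not an SSB | counted (juice named) | separate | separate |
| Diet soda | not an SSB | can be counted | separate | separate |
| Tea | only if sweetened | named, unqualified | sweetened and unsweetened split | diet and sweetened split |
| Vending purchase of an SSB | included | not asked | not applicable | not applicable |

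The protocol gives no effect size, variance or power for this outcome, so there is no planned figure to reproduce. What follows is an illustration on assumed inputs.

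Take 100 children who would be counted by item 4 without the intervention. Let

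- f = share of them with only non-SSB sweet drinks (not in the protocol; 20% and 40% assumed),
- r = true relative reduction in children with an SSB (30% assumed),
- q = share of children giving up an SSB who bring a counted non-SSB instead,
- g = relative reduction among the non-SSB children.

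Apparent relative reduction = (1 − f) × r × (1 − q) + f × g. True fall in SSB children = 100 × (1 − f) × r.

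| Scenario | f | Tally, from 100 to | Apparent reduction | Fall in tally vs true fall in SSB children |
|---|---|---|---|---|
| A. Non-SSBs unaffected (q = 0, g = 0) | 20% | 56 + 20 = 76 | 0.80 × 0.30 = 24% | 24 vs 24 |
| | 40% | 42 + 40 = 82 | 0.60 × 0.30 = 18% | 18 vs 18 |
| B. Half of quitters substitute (q = 0.5, g = 0) | 20% | 56 + 20 + 12 = 88 | 0.24 × 0.5 = 12% | 12 vs 24 |
| | 40% | 42 + 40 + 9 = 91 | 0.18 × 0.5 = 9% | 9 vs 18 |
| C. Non-SSBs fall in proportion (q = 0, g = 0.30) | 20% | 56 + 14 = 70 | 0.24 + 0.06 = 30% | 30 vs 24 |
| | 40% | 42 + 28 = 70 | 0.18 + 0.12 = 30% | 30 vs 18 |

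In A the relative effect shrinks but the absolute difference is right and only noisier. In B both are too small. In C the relative effect is right, while the absolute fall in the tally includes drinks that are not SSBs.

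A rough translation to power: "The study is a group randomized trial with n=28 centers", and the site list attached to Appendix E shows 14 sites of each fountain type, taken here as 14 per arm. With a normal approximation, two-sided alpha 0.05 and an assumed between-center coefficient of variation of 0.3, power is 75% for an apparent 30% reduction, 56% for 24% and 18% for 12%. At a coefficient of variation of 0.5, power for 30% and 24% is 36% and 25%. These figures show only that the scenarios differ materially.

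**The case against.** The strongest reply is that the main instrument is not visible. The form is a backup, the text wording is not reproduced, and training may have covered the distinction. This stands as a limit on certainty. The indications still favor matching wording: both have six questions, and Appendix E describes the site leaders' daily report in terms that match the form's items and calls this one a sugary drink tally. On the other hand, the Procedures section lists only four questions. If the texts do differ from the form, backup days use a different definition, which also needs reconciling.

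A second reply is that a short, lay item suits liaisons who report every day, and that telling 100% juice from a juice drink is hard even for trained observers, who are told to judge by appearance. This is a fair reason for a simple item. It does not justify calling the result SSB.

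Some stronger readings are tempting and do not hold:

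- A reader might infer that unsweetened tea is counted by instruction. The capitalized qualifier is sweet, which on a literal reading screens it out; unqualified tea is ambiguous, no more.
- A reader might infer that the other instruments also sort smoothies. Neither has a smoothie category. They have mixed categories of their own: plain with flavored milk in Appendix D, all coffee drinks together in Appendix E.
- A reader might infer that the tally cannot be compared with the observers' counts because the categories differ. The finer categories could be summed to approximate item 4. The real limits are that observations occur only at post, last 30 minutes and cover everyone in view.

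**Conclusion.** The mismatch is real and rests on the text alone: as shown, the item can count 100% juice and sweet-tasting diet drinks toward an SSB outcome, leaves tea ambiguous, and does not ask about vending purchases. The numerical consequence is conditional. A true 30% reduction appears as 24% or 18% if an assumed 20% or 40% of counted children have only non-SSBs that do not change, and as 12% or 9% if, in addition, half of those giving up SSBs substitute. It stays at 30% if the other drinks fall in proportion. A reader might conclude that the SSB effect is certainly diluted or hidden. The documents do not support this, because they give neither the share of non-SSBs nor any information on how those drinks respond to the intervention. This is a point that should be fixed. It does not by itself invalidate the trial.

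**What to change.** Align item 4, the matching text question and the quick guide with the definition in the Measures section, keeping its restriction to drinks brought in or bought from vending. For example: *How many kids brought in, or bought from the vending machine, a drink with added sugar (regular soda, fruit drinks, sports drinks, sweetened tea, etc.)? Do not count 100% juice, diet drinks or unsweetened tea.* Use identical wording in all three measurement periods. An item about drinks children merely had would be too broad, because it could take in drinks supplied by the center.

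If baseline was already collected under the current wording, keep that wording at midpoint and post so that the periods remain comparable, rename the outcome as children bringing in any sweet drink, and claim no effect on SSBs specifically. This branch is likely to apply: baseline was scheduled for July/August 2017, before the installations, and the protocol already describes post-installation water testing in the past tense.

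The cost is a few lines in one question, one form and one guide, plus a mention in training. The downside of the exclusions is that liaisons will sometimes misclassify 100% juice and juice drinks. The downside of renaming is a less specific primary outcome that leaves out vending purchases.

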Sports drinks like Gatorade, Vitamin water, Powerade (do NOT include diet)	0	0	0	0	0	0	0	0	0	0	0	0	0
Diet fruit, energy, or sports drinks like diet cranberry drink, Red Bull Sugarfree, Powerade Zero	0	0	0	0	0	0	0	0	0	0	0	0	0
Diet soda or pop like Diet Coke or Sprite Zero	0	0	0	0	0	0	0	0	0	0	0	0	0
Regular soda or pop like Coke, Pepsi, Sprite, Sunkist, grape soda (do NOT include diet)	0	0	0	0	0	0	0	0	0	0	0	0	0
Pre-sweetened coffee like mocha or Frappuccino (do NOT inlcude diet or plain coffee you add sugar to)	0	0	0	0	0	0	0	0	0	0	0	0	0
Unsweetened coffee (black or with milk)	0	0	0	0	0	0	0	0	0	0	0	0	0
Pre-sweetened tea like Arizona or Snapple (do NOT include diet or plain tea you add sugar to)	0	0	0	0	0	0	0	0	0	0	0	0	0
Unsweetened or diet tea like plain tea, diet Arizona, diet Snapple	0	0	0	0	0	0	0	0	0	0	0	0	0
Plain or flavored milk (do NOT include milk in cereal)	0	0	0	0	0	0	0	0	0	0	0	0	0
Unsweetened bottled or tap water (including sparkling)	0	0	0	0	0	0	0	0	0	0	0	0	0

BE SURE TO ANSWER THESE QUESTIONS FOR ALL BEVERAGES YOU DRANK

2

Hydrate Philly Water Fountain Observation Cheat Sheet

- 1. Arrive at recreation center. Find site leader and ask for today's program attendance.
- 2. (Intervention sites only) Record 'challenge game' and 'program bottle count'.
- 3. Take photos of water source at 10 feet and close up.
- 4. (If time allows) test time to fill bottle/cup from bottle filler and/or spigot.
- 5. Immediately before observation period begins, record flow meter reading and take photo.
- 6. As observation period begins, count initial tally of total site visitors.
- 7. Complete observation period.
- 8. Immediately after observation period ends, record flow meter reading and take photos.
- 9. If you did not do so earlier, test time to fill bottle/cup now.
- 10. Text photo of completed observation form to [name] at [contact].

Hydrate Philly Water Fountain Observation Protocol

Overview of Observation Design

- 1. All 28 study sites will receive 5 observations (1 each weekday) lasting 30 minutes each (see Appendix A for schedule).
- 2. Observations will occur over 2-3 weeks by a single RA at each site. RAs will train to reliability using a gold standard measurement and a 2nd RA will conduct intermittent 2nd observations overlapping with the 1st RA for inter-rater reliability calculation purposes.
- 3. Intervention and control matched pair sites will be observed at the same time period.

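### Staff SSB consumption is scored through total beverage energy, which also counts 100% juice and plain milk and so is not an SSB measure

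*Protocol*

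**What the plan says.** The Measures section of the protocol lists "Staff SSB consumption (secondary outcome/mediator") among the outcomes. In each measurement period "the staff liaison will complete the Beverage Intake Questionnaire (BEVQ-15"), given in Appendix D, and the answers are used to "estimate staff SSB and water consumption using ounces of water and total energy intake from beverages". No other score for staff SSB is named.

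Appendix D asks how often and how much of each beverage was drunk in the past month, one row per beverage type. It has one row for 100% fruit juice and another for sweetened fruit drinks, and it pools plain and flavored milk in one row.

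The pre-sweetened coffee row carries the instruction "do NOT inlcude diet or plain coffee you add sugar to", and the pre-sweetened tea row "do NOT include diet or plain tea you add sugar to". The other coffee row is "Unsweetened coffee (black or with milk"), and the other tea row is for unsweetened or diet tea. The form ends by telling the respondent to answer for every beverage drunk. Under Procedures, the liaison is to "fill out a 15-question survey on their own beverage consumption once per measurement period".

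**The concern.** The named outcome is sugar-sweetened beverage consumption, but the only metric that can stand for it is energy from all beverages. These are different quantities. The title of the second questionnaire paper in the protocol's own reference list names them as two separate things.

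A program that discourages SSBs may lead staff to replace soda with water, but also with juice or milk. Total energy responds to the first switch and may not respond to the second. Because the variable is also a candidate mediator, a score that mixes SSB with other energy would weaken any statement that staff SSB intake lies on the path to the center outcomes.

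A smaller matter is coffee or tea that the respondent sweetens. The form keeps these drinks out of the pre-sweetened rows and shows no other row that fits them, so their added sugar enters neither an SSB score nor the energy total.

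**Working it through.** **1. Metric against outcome.** The scoring sentence names two estimands (staff SSB, staff water) and two metrics (ounces of water, total beverage energy). Ounces of water can only serve water. Total beverage energy is what remains for SSB.

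**2. What the total contains.** The rows visible in Appendix D, without the example line, are:
- sugar-sweetened, 6: sweetened fruit drinks, energy drinks, sports drinks, regular soda, pre-sweetened coffee, pre-sweetened tea;
- energy-bearing but not clearly SSB, 2: 100% juice, and plain or flavored milk;
- diet, unsweetened or water, 5: diet fruit/energy/sports drinks, diet soda, unsweetened coffee, unsweetened or diet tea, water.

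6 + 2 + 5 = 13 visible rows. An SSB score can be built from the first group with no new data.

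**3. Size for a soda-to-juice switch.** The documents give no energy densities. Assume s = 12 kcal/oz for soda, j = 14 kcal/oz for juice, and an equal volume v = 12 oz/day.
- Change in SSB energy: −v × s = −12 × 12 = −144 kcal/day.
- Change in total beverage energy: v × (j − s) = 12 × (14 − 12) = +24 kcal/day.
- Share of the SSB fall hidden by the total: j/s = 14/12 = 117%.

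If j/s lies anywhere from 0.8 to 1.2, the total hides 80% to 120% of the fall. It then moves by −28.8 to +28.8 kcal/day, against a true −144.

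The fountain list attached to the observation protocol shows 14 sites of each fountain type. Taking these as the arms, with one liaison each, three such switchers in one arm change its mean SSB energy by 3 × (−144)/14 = −30.9 kcal/day and the score by 3 × 24/14 = +5.1 kcal/day.

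Unchanged juice intake adds energy too: 8 to 20 oz/day at 14 kcal/oz is 112 to 280 kcal/day of non-SSB energy in the score.

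**4. Self-sweetened coffee and tea.** Assume 16 kcal per teaspoon, 1 to 3 cups a day and 1 to 3 teaspoons a cup. The sugar not recorded is 1 × 1 × 16 = 16 to 3 × 3 × 16 = 144 kcal/day per affected person. Three affected liaisons, all in one arm of 14, would lower its mean by 48/14 = 3.4 to 432/14 = 30.9 kcal/day. The documents give no standard deviation or target difference to judge this against.

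**5. The stated count of 15.** The visible rows give 13, or 14 with the example line, or 26 at two questions per row. None is 15. But each row carries 13 bubbles while only 12 column headings survive (six frequencies, six amounts). Text has therefore been lost from this table, and the count cannot be settled from it.

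**The case against.** **Scoring belongs in the SAP.** The form records frequency and amount by beverage, so an SSB-only score needs no redesign, and detailed scoring often sits in an SAP, which is not at hand. It stands that the remedy is small. It does not remove the point, because the protocol does not leave the metric open: it names one, and that one does not match the outcome.

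**Total energy is not uninformative.** It falls when soda is replaced by water or a diet drink. That stands. The failure is limited to switches into other energy-bearing drinks, and the documents do not say how common those are.

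**Juice may count as an SSB here.** The paper backup form in Appendix B lists juice among sweet drinks in the children's tally. But the staff form separates 100% juice from sweetened fruit drinks, and the fountain observation form gives it its own category. Plain milk would remain in the total on either reading.

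**Stronger readings a reader might infer.**
- That the coffee and tea gap biases the trial. The documents do not support this. Leaving out self-sweetened drinks may be a deliberate boundary, and some respondents may enter such tea under plain tea, which captures its volume but not its sugar. Nothing shows that the form differs by arm or period, and a constant omission lowers the level without by itself distorting a randomized contrast. A switch from a 12 oz soda (144 kcal) to one self-sweetened cup (16 to 48 kcal) would be a real fall in sugar, so scoring it as improvement has the right direction.
- That the form is two items short. A lost row cannot be excluded, and it could even be the row that seems to be missing.

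**Conclusion.** The point holds for the scoring. Total beverage energy, the only metric in the protocol that can represent staff SSB, includes energy from 100% juice and plain milk and is not an SSB measure. Under the assumed densities, a like-for-like switch from soda to juice hides the whole fall in SSB energy (117%; 80% to 120% over the range shown). How often such switches occur is unknown, so no bias in the arm comparison is claimed.

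The coffee and tea wording is a secondary matter of clarity: the form asks for all beverages yet, as available, shows no row that fits these drinks. It does not establish that the outcome is biased. The count of 15 is a query to check and not a finding.

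Neither primary outcome is touched.

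**What to change.** **Scoring.** In Measures, define staff SSB consumption as ounces and energy from the six sweetened rows: sweetened fruit drinks, energy drinks, sports drinks, regular soda, pre-sweetened coffee and pre-sweetened tea. Report total beverage energy separately under its own name. Say that flavored milk falls outside the SSB score because the form pools it with plain milk. The cost is a few sentences and a scoring rule, and it can be applied to forms already completed.

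**Self-sweetened coffee and tea.** State that the SSB score leaves these drinks out, or say where they are recorded. Add rows only if no baseline forms have been collected. Baseline was set for July/August 2017, and the attached water testing protocol is dated September 2017, so baseline forms probably exist. In that case keep the score built from the rows common to all periods. New rows after baseline would break comparability over time and depart further from the cited instrument.

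**Count.** Check the stated 15 questions against the original form, and correct whichever is wrong only if the two differ there.
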